#### **3.2.2.1. Baseline Visit – Day 0**

The assessments and procedures to be performed during the Baseline (Day 0) visit are listed in the Schedule of Events (Table 6). [REDACTED] will be performed after the controlled fasting challenge is complete to avoid having to replace the sensor prior to the fasting challenge. (Section 8.1.4).

Subjects will participate in a controlled fasting challenge. The Investigator or delegated sub-investigator will review the results of all laboratory assessments performed on the first day of the inpatient visit, including cortisol. Subjects should wear their CGM device throughout the fasting challenge, and should not change the sensor prior to the assessment. Before the controlled fasting challenge begins, the study site will provide dinner for the subject. The dinner meal will be personalized for each subject and will include a target carbohydrate range and overall composition in protein, fats and dietary fibers that is as close as possible to the subject's most current dinner dietary prescription. The content of the dinner and quantities consumed will be recorded.

After dinner, subjects will be given an oral dose of cornstarch equivalent per their most recent cornstarch prescription at approximately the same time that they typically take it, but no later than 3 hours post dinner. The time of ingestion of prefasting cornstarch and the amount consumed will be recorded. After the cornstarch is ingested, the controlled fasting challenge will begin, and the start time will be recorded accordingly. If subjects do not receive cornstarch overnight, the fasting test will begin after they complete their dinner. Subjects will be instructed to minimize activity after they finish eating dinner until the end of the fasting challenge.

During the fast, subjects may not ingest any food or drink other than water. The controlled fasting challenge will end when the subject's glucose level decreases to < 54 mg/dL (< 3.0 mmol/L) or subjects experience signs and symptoms of hypoglycemia, or the fast reaches 15 hours without hypoglycemia, whichever occurs first. The stop time of the controlled fasting challenge will be recorded. At the end of the controlled fasting challenge, the subject's hypoglycemia should be treated per the institution's standard procedure, which may include providing the subject with a meal, cornstarch, or IV glucose, if medically indicated.

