Before the controlled fasting challenge begins, the study site will provide dinner for the subject. The dinner meal will be personalized for each subject, and will include a target carbohydrate range and overall composition in protein, fats and dietary fibers that is as close as possible to the subject's most current dinner prescription, but not higher in carbohydrate content than the dinner consumed at their baseline fasting challenge. The start and stop time of the dinner meal and its full dietary composition including amount of carbohydrates consumed will be recorded. After dinner, subjects will be given an oral dose of cornstarch equivalent per their most recent cornstarch prescription, at approximately the same time that they typically take it, but no later than 3 hours post dinner. The amount of cornstarch administered should not be higher than that consumed by the subject at the baseline fasting challenge. The time of ingestion of prefasting cornstarch and the amount consumed will be recorded. After the cornstarch is ingested, the controlled fasting challenge will begin, and the start time will be recorded accordingly. If a subject does not receive cornstarch before going to bed at the time of the CFC, the fasting challenge will start after they complete their dinner. Subjects will be instructed to minimize activity after they finish eating dinner until the end of the controlled fasting challenge.

During the fast, subjects may not ingest any food or drink other than water. The controlled fasting challenge will end when the subject's glucose level decreases to  $< 54$  mg/dL ( $< 3.0$  mmol/L) or when the subjects experience signs and symptoms of hypoglycemia, or when the fast reaches 15 hours without hypoglycemia, whichever occurs first. The stop time of the controlled fasting challenge will be recorded. At the end of the controlled fasting challenge, the subject's hypoglycemia should be treated per the institution's standard procedure, which may include providing the subject with a meal, cornstarch, or IV glucose, if medically indicated.

In cases where the controlled fasting challenge is terminated prematurely before the subject reaches a glucose level of < 54mg/dL or without the subject experiencing signs and symptoms of hypoglycemia, or due to any deviation in the fasting challenge protocol, an ad hoc fasting challenge may be scheduled within 6 weeks from the scheduled fasting challenge.

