Blood samples for STAT analysis of glucose and lactate will be collected through an indwelling catheter (central or peripheral) at the following time points:

- At the beginning of the fast (ie, immediately after the post-dinner dose of cornstarch, or immediately after dinner for subjects who do not take a post-dinner dose of cornstarch)
- Approximately every 60 minutes ( $\pm$  5 minutes) until the glucose level decreases to  $\leq$  70 mg/dL ( $\leq$  3.9 mmol/L)

- Approximately every 30 minutes ( $\pm$  5 minutes) until the glucose level decreases to  $< 54$  mg/dL ( $< 3.0$  mmol/L) or when the subjects experience signs and symptoms of hypoglycemia, or when the fast reaches 15 hours without hypoglycemia, whichever occurs first

Samples should be prepared and transported to the local laboratory in accordance with the site's standard procedures. To ensure the safety of the study subjects, results from these tests should be available within 30 minutes after the blood sample collection. Capillary glucose will be performed at the same time points as blood samples for STAT analysis of glucose and lactate. Results of the capillary glucose and readings from CGM at corresponding time points will be noted on a controlled fasting challenge results sheet.

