8.5. Efficacy Analysis

8.5.1. Symptom-Free Euglycemia

The time (in minutes) to the first hypoglycemic event (defined as glucose <60 mg/dL [<3.3 mmol/L]) during a controlled fasting challenge at baseline (Day 0), Week 12, 24 and 52, and the change from baseline in time (in minutes) to first hypoglycemic event at Weeks 12, 24, and 52 will be summarized. If the controlled fasting challenge has to be stopped due to symptomatic hypoglycemic event, or the subject is administered intervention (e.g., cornstarch), the time to the first hypoglycemic event will be defined as the time to the controlled fasting challenge is terminated. If there is no hypoglycemic event during the fasting challenge, the time will be censored at the maximum evaluable time (15 hours).

A listing of the controlled fasting challenges and the glucose, lactate, and other local lab parameters (cortisol, free fatty acids, glucagon etc.), and capillary glucose levels (if available) collected during the controlled fasting challenges will be provided. Use of cornstarch and carbohydrates in the dinner prior to controlled fasting challenge and change from baseline will be summarized by visit.

In addition, plots for individual patient profile of controlled fasting challenge hours, plots for individual patient profile of glucose and lactate during controlled fasting challenges will be presented by study visits.

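### SAP 8.5.1 gives two rules for the time to first hypoglycemic event and no order between them, so a later challenge stop time can replace an earlier qualifying glucose time

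*SAP*

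**What the plan says.** SAP 8.5.1 starts from glucose: "The time (in minutes) to the first hypoglycemic event (defined as glucose <60 mg/dL". It then gives a second rule. The trigger is a stop for symptoms, or treatment: "or the subject is administered intervention (e.g., cornstarch), the time to the first hypoglycemic event will be defined as the time to the controlled fasting". In full, the result is "the time to the first hypoglycemic event will be defined as the time to the controlled fasting challenge is terminated". If there is no event, "the time will be censored at the maximum evaluable time (15 hours".

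The second rule does not say that the intervention must be given during the fast, must be the reason for stopping, or must come before any qualifying glucose. Nothing says which rule wins when both apply.

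On the protocol side, the challenge ends when "glucose level decreases to < 54 mg/dL (< 3.0 mmol/L) or subjects experience signs and symptoms of hypoglycemia", or at 15 hours (Protocol 3.2.2.1, repeated in 8.1.1). Once it has ended, treatment where medically needed follows: "subject's hypoglycemia should be treated per the institution's standard procedure, which may include providing the subject with a meal, cornstarch, or IV glucose" (Protocol 8.1.1). For the STAT glucose samples, "results from these tests should be available within 30 minutes after the blood sample collection" (Protocol 8.1.1).

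**The concern.** A challenge that ends on a low glucose and is then treated with cornstarch satisfies both rules. The first times it at the low glucose, the second at the stop. A challenge stopped for symptoms after a glucose already below the analysis threshold also satisfies both, with no need to read the word intervention broadly.

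The change from baseline in this time is the only secondary endpoint, and it is the one tied to the objective of establishing a dose that keeps fasting glucose up. Two programmers could derive different values from the same record, and following the second rule exactly puts the event later than the SAP's own first event. Summaries are by cohort of 3 subjects (SAP 8.1), so a shift in one subject is visible in the cohort figure.

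**Working it through.** **1. Inputs.** SAP 8.5.1: event below 60 mg/dL; second rule uses the termination time; limit 15 h × 60 = 900 min. Protocol 8.1.1: stop below 54 mg/dL, at symptoms, or at 15 hours; samples about every 60 min until glucose is at or below 70 mg/dL, then about every 30 min; result within 30 min of the draw. The plan states no figure for this gap, so there is none to reproduce.

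**2. Symptom limb alone (hypothetical subject).** Glucose is 58 mg/dL at 300 min. The fast continues, because 58 is not below 54. Symptoms stop it at 330 min. First rule: 300. Second rule: 330. Both apply on their plain meaning, and the later time is not the SAP's first event.

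**3. Thresholds equal (60/60 or 54/54).** The sample that qualifies as the event also ends the challenge. Gap = stop − draw = L, where L is the wait for the result and 0 ≤ L ≤ 30. So the gap is 0 to 30 min. It is 0 if the site records the draw time as the stop time, or acts on the capillary or CGM reading taken at the same time point.

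**4. Event below 60, stop below 54.** Glucose must fall a further 6 mg/dL, which takes 6/r × 60 min at r mg/dL per hour, subject to the sampling grid. The decline is assumed linear from a starting glucose of 85 to 120 mg/dL. Neither the rates nor the starting values are in the documents.

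| Assumed r (mg/dL/h) | 6/r × 60 (min) | Gap on sampling grid, L = 0 | Gap, L = 30 |
|---|---|---|---|
| 3 | 120 | 0 to 120 | 0 to 150 |
| 6 | 60 | 60 | 90 |
| 12 | 30 | 30 | 60 |
| 20 | 18 | 0 to 30 | 30 to 60 |

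The zeros at 3 mg/dL/h are fasts that reach 15 hours.

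**5. Effect on the change from baseline.** If the stop time replaces the glucose time by b minutes at baseline and f minutes at follow-up, the change moves by f − b.
- Same kind of ending and same lag: f = b, shift 0.
- Baseline ended by glucose (draw at 240, stop at 270, b = 30), follow-up reaches 900 (f = 0): 900 − 240 = 660 against 900 − 270 = 630, a shift of −30, which understates benefit.
- Baseline under a 60 mg/dL stop with L = 30 (b = 30), follow-up under a 54 mg/dL stop at the assumed 6 mg/dL/h with L = 30 (f = 90): shift +60, which overstates benefit. Amendment 6 lowered the stop from 60 to 54, so this pairing is possible. The documents do not say how many subjects have it.

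**6. Scale.** Against the 7-hour cornstarch median cited in Protocol 1.3.1: 30/420 = 7.1%. Against the 660-minute change above: 30/660 = 4.5%. A 30-minute shift in one subject moves a mean of 3 by 30/3 = 10 min.

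**7. Event status.** A subject who completes 15 hours and is then given cornstarch literally meets the intervention clause. The value stays at 900 min, but the record would change from censored to event.

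**The case against.** The strongest case is that the SAP never says the stop time overrides an earlier glucose. The clause pairs a stop forced by symptoms with an intervention, and the ordinary reading is a challenge cut short before a low reading. Protocol treatment is given after the challenge has ended, so it does not cause the ending, and cornstarch is only one option. All of this stands. A reader might infer that the SAP deliberately resets every treated challenge to its stop time; the text supports only an unordered pair of rules that permits that result.

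A reader might also infer a routine 30-minute delay. The documents do not support this. Neither timing the event at the draw nor waiting for the STAT result before stopping is protocol text; 30 minutes is the limit set for the result, and capillary and CGM readings are available at the same time points. Nor should the gap be set against the 2 to 4 hours in Protocol 1.3.1 (12.5% to 25%): that figure is for patients without cornstarch, while the challenge usually starts after a cornstarch dose.

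The endpoint is only summarized, with no test, alpha or power. Protocol 1.3.1 assumes intraperson variability of ±2 hours, and samples are 30 to 60 minutes apart. The SAP lists and plots the individual challenges, so a discrepancy could be seen. These points limit the importance. They do not supply the missing order, and the symptom-limb example in step 2 does not depend on how intervention is read.

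**Conclusion.** The point holds as an ambiguity with a real consequence, not as a stated override. SAP 8.5.1 has two event-time rules without precedence, and the rule as written can replace an earlier qualifying glucose time with a later stop time. The size is 0 to about 30 minutes when the event and stop thresholds agree, and the upper end requires that the stop waits for the laboratory. With the SAP's 60 mg/dL event and the protocol's 54 mg/dL stop it can reach roughly 150 minutes, on assumed linear declines of 3 to 20 mg/dL per hour. Most of that larger gap comes from the threshold mismatch; the missing order is what lets it into the endpoint. The shift cancels in the change from baseline only when both challenges end in the same way with a similar lag, and its direction depends on the pairing. No error rate is affected. It should be corrected before the endpoint is derived.

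**What to change.** Replace the second rule in SAP 8.5.1 with wording such as:

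> Time to first hypoglycemic event is the earlier of (a) the collection time of the first glucose below the analysis threshold and (b) the challenge stop time, when the challenge is stopped for symptoms, or an intervention is given during the fast, before any such glucose. Treatment given after the challenge has ended, including after a completed 15-hour fast, changes neither the time nor the event or censoring status.

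Reconcile the thresholds at the same time: SAP 8.5.1 uses below 60 mg/dL, while the protocol (Sections 2, 8.1.1 and 10.2.3.1) and SAP 4.2 use below 54 mg/dL. SAP 9 lists no change from the protocol's analyses. Until this is settled, the analysis threshold in (a) is undefined, and the new sentence alone does not fix the event time.

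The cost is a short SAP edit and a programming check. Protocol 8.1.1 requires the start and stop times to be recorded. It sets a sampling schedule but does not expressly require actual draw times to be recorded, so their presence in the data should be confirmed. The planned plots of glucose during the challenge suggest they are held. No new data collection appears necessary.

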**Weeks 12 and 24 (Inpatient Visits)**

Subjects will be admitted to the study site or hospital for approximately 24 hours for all assessments. Each subject will remain on his or her prescribed diet for the duration of each inpatient stay.

If the subject is off steroid treatments and the Investigator considers it is safe to proceed with the inpatient Week 12 visit, approximately 1 week before the Week 12 visit, a blood sample for measurement of ACTH and cortisol levels will be collected if possible. A blood sample for measurement of lipid levels will be collected on the morning of hospital admission at approximately the same time as collected on Day 0. The sample should be collected at least 2 to 4 hours after the subject's last meal. If the subject continues to be on steroid regimen and the Investigator determines that it is not safe to proceed with the CFC, the Week 12 visit will become an outpatient visit. Investigators should try to complete an ad hoc CFC assessment as soon as the subject has completed steroid treatment and within 8 weeks of the Week 12 visit, as an unscheduled visit.

A urine pregnancy test will be performed (for females of childbearing potential only). Blood samples will be collected for clinical laboratory assessments (clinical chemistry [including liver function tests], hematology, and coagulation panel), AAV8 neutralizing antibody testing, AAV8 binding antibody IgG testing, cell-mediated immune response to AAV8 and G6Pase testing, anti-G6Pase antibody testing (Week 12 only), and vector genome determination. A urine sample will be collected for urinalysis. A second blood sample will be collected for liver function tests and sent to the local laboratory (STAT sample) through Week 12, or longer if clinically indicated. Saliva, urine, and stool samples will be collected for assessment of vector shedding through Week 12. If still positive at the Week 12 visit, vector shedding samples will continue to be collected during scheduled study visits until at least 3 consecutive negative results are obtained from each sample matrix.

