#### **8.1.1. Symptom-Free Euglycemia (Controlled Fasting Challenge)**

The subject's ability to maintain symptom-free euglycemia during a controlled fasting challenge will be assessed at time points specified in the Schedule of Events. However, if clinically indicated, the controlled fasting challenge can also be performed at an unscheduled visit.

The controlled fasting challenge requires a 24-hour inpatient stay in a hospital or research facility and will be performed after all other study visit assessments (except [REDACTED]) have been completed and the required laboratory assessments (as specified below) have been reviewed by the Investigator (or a subinvestigator assigned to review results and make clinical decisions per the site delegation log). Subjects should wear their CGM device throughout the fasting challenge, and should not change the sensor prior to the assessment.

If a subject is suspected to have HPA axis impairment (eg, due to prolonged steroid treatment; may be confirmed by morning cortisol or stimulation tests), the fasting challenge may have to be rescheduled to a later date in order to ensure subject safety and provide interpretable results.

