8. STATISTICAL METHODS OF ANALYSES

8.1. General Principles

Continuous variables will be summarized by number of subjects and mean, standard deviation (SD), standard error (SE), median, Q1, Q3, minimum, and maximum values. Categorical variables will be summarized by number and percentage of subjects. All summary tables will be presented by scheduled study visit and no analysis windows will be used, unless specified otherwise. All the summary tables will be presented by dosing cohort of DTX401 and overall, unless specified otherwise. The dosing cohorts are:

- Cohort 1: Dose 1 $(2.0 \times 10^{12} \,\text{GC/kg})$ with a reactive steroid regimen (prednisone starting dose of 40 mg/day)
- Cohort 2: Dose 2 $(6.0 \times 10^{12} \,\text{GC/kg})$ with a reactive steroid regimen (prednisone starting dose of 40 mg/day)
- Cohort 3: Dose 2 $(6.0 \times 10^{12} \,\text{GC/kg})$ with an optimized reactive steroid regimen (prednisone starting dose of 60 mg/day)
- Cohort 4: Dose 2 $(6.0 \times 10^{12} \text{ GC/kg})$ with a prophylactic steroid regimen

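### SAP 8.5.1 records 15 h for an event-free fasting challenge without requiring a completed fast, so an early event-free stop is overstated and its valid repeat may be left out of the visit table

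*SAP*

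**What the plan says.** SAP 8.5.1 tabulates time to first hypoglycemic event at Day 0 and Weeks 12, 24 and 52, and its change from baseline. Besides the glucose threshold it has two rules.

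- If the challenge is stopped for symptomatic hypoglycemia, "or the subject is administered intervention (e.g., cornstarch), the time to the first hypoglycemic event will be defined as" the time at which the challenge ended.
- "If there is no hypoglycemic event during the fasting challenge, the time will be censored at the maximum evaluable time (15 hours").

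SAP 8.1 governs how these values are presented: "Continuous variables will be summarized by number of subjects and mean, standard deviation (SD), standard error (SE), median, Q1, Q3, minimum, and maximum values". It also sets the visit rule: "All summary tables will be presented by scheduled study visit and no analysis windows will be used, unless specified otherwise". SAP 8.5.2 makes an exception to that rule for cornstarch, with a window of 14 days either side and a fallback to unscheduled visits. SAP 8.5.1 makes none.

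Protocol 8.1.1 ends a fast at low glucose, at symptoms, or at 15 h. It then deals with other endings: "In cases where the controlled fasting challenge is terminated prematurely before the subject reaches a glucose level of < 54mg/dL", or without symptoms, or for any deviation from the procedure, "an ad hoc fasting challenge may be scheduled within 6 weeks from the scheduled fasting challenge".

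**The concern.** The no-event rule depends only on the absence of an event, not on how long the subject was observed. A fast stopped at 5 h for a procedural reason, with normal glucose, shows only that the time exceeds 5 h. The rule enters 15 h. SAP 8.1 plans means, standard deviations and quartiles with no method for censored values, so in practice 900 min is averaged as if observed.

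Protocol 8.1.1 offers a remedy, the ad hoc repeat, but the SAP does not say that the repeat replaces the aborted test. If the repeat is recorded as an unscheduled visit, as its ad hoc character suggests, the SAP 8.1 default keeps the aborted test in the table and omits the valid one.

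At stake is the summary of the only secondary endpoint, in cohorts of three where one value carries a third of the mean. The change from baseline is overstated if this happens after baseline, and understated if it happens at baseline.

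**Working it through.** **Inputs**

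- Cap: 15 h × 60 = 900 min (SAP 8.5.1). This agrees with the 15 h end condition in protocol 8.1.1.
- Sample size: 4 cohorts × 3 subjects = 12, which reproduces SAP 3.5.
- Expected post-treatment fast of at least 8 h = 480 min, and intraperson variability of ±2 h = 120 min (protocol 1.3.1).
- Stop time t: not in the documents. Assumed values of 120, 300, 480 and 720 min.

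**Which endings reach the 15 h rule?**

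- Glucose below the event threshold: time of that event.
- Symptomatic stop: termination time.
- Intervention given: termination time, labelled an event. If the subject had no low glucose or symptoms and was simply fed after an aborted fast, the value is usable as a lower bound but the label is wrong. The SAP gives cornstarch as an example of intervention and does not define the term.
- 15 h completed without an event: 900 min, correctly.
- Early stop with no low reading, no symptoms and no intervention: 900 min, although only t minutes were observed.

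The width of the last case depends on the threshold. SAP 8.5.1 uses < 60 mg/dL, while SAP 4.2 and protocol section 2 use < 54 mg/dL. At < 60, a fast stopped after a reading of 54 to 59 is already an event. At < 54 it is not.

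**Size for one such subject**

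Maximum overstatement = 900 - t. Maximum shift in a mean of n subjects = (900 - t)/n.

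| Stop t (min, assumed) | 900 - t | n = 3 | n = 12 |
|---|---|---|---|
| 120 | 780 | 260 | 65 |
| 300 | 600 | 200 | 50 |
| 480 | 420 | 140 | 35 |
| 720 | 180 | 60 | 15 |

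The cohort shift exceeds the protocol's 120 min variability when (900 - t)/3 > 120, that is, for t < 540 min (9 h).

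**Illustration (assumed values)**

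Two subjects have events at 480 and 600 min, and a third is stopped event-free at 300 min.

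- SAP rule: (480 + 600 + 900)/3 = 660, median 600.
- Stop time: (480 + 600 + 300)/3 = 460, median 480.
- Test treated as missing: (480 + 600)/2 = 540.

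With times capped at 15 h, the true mean lies between 460 and 660. Dropping the test is not a safe middle course. For a stop at 720 min it still gives 540, although the data already guarantee at least (480 + 600 + 720)/3 = 600.

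**Timing of a repeat**

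The limit is 6 × 7 = 42 days after the scheduled challenge. A repeat at that limit would fall outside a 14-day window like the one in SAP 8.5.2, so copying that window would not be enough.

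**The case against.** The best defence is that the 15 h sentence was written with completed fasts in mind. It speaks of the maximum evaluable time, and a full 15 h is the only event-free ending among the protocol's three standard ones. The preceding sentence already sends symptomatic and treated stops to the termination time. No test or decision rule uses these means, and SAP 8.5.1 plans listings and individual plots in which an early stop could be seen. The table shells are kept separately and may hold further conventions. All of this narrows the problem and limits the harm. It does not supply the missing condition, and protocol 10.2.3.1 leaves the analysis details to the SAP.

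A reader might infer more, in four ways that the documents do not support.

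- That every event-free or interrupted challenge is credited with 15 h. Symptomatic and treated stops are not, and completed fasts are credited correctly.
- That the SAP has no rule for off-schedule challenges. The SAP 8.1 default implies one: they stay out of visit tables.
- That omitting a steroid-deferred Week 12 challenge is an error. The protocol synopsis allows it "within 8 weeks of the Week 12 visit, as an unscheduled visit", hence as late as Day 84 + 56 = 140, only 28 days before Week 24 (Day 168). The endpoint is defined at 12, 24 and 52 weeks, so either choice is defensible. A challenge postponed for suspected adrenal-axis impairment ("the fasting challenge may have to be rescheduled to a later date in order to ensure subject safety and provide interpretable results") likewise raises only the question of visit assignment, since there is no competing second value.
- That the Cohort 3 Week 32 fasting times in protocol 1.3.1 show these pathways in use. Week 32 is Day 224, which is 56 days after Week 24 (repeat limit 42) and 140 days after Week 12 (deferral limit 56). Protocol 8.1.1 separately permits unscheduled challenges when clinically indicated, and no reason is given for this one.

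**Conclusion.** The point holds in a narrow form and is worth fixing before the tables are produced. Followed literally, SAP 8.5.1 gives a wrong value to a challenge that stops early with no reading below the event threshold, no symptoms and no intervention. The error is at most 900 - t for the subject and (900 - t)/3 for a cohort mean: 60 to 260 min for one such stop between 720 and 120 min. Together with SAP 8.1, it can also keep that value in place of a valid repeat.

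This rests on assumed stop times, on one affected subject per cohort, and on the repeat being recorded as unscheduled. The figures show how sensitive a three-subject mean is. They are not an expected bias, because the documents do not say how often such stops occur. The consequence is confined to descriptive summaries.

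**What to change.** In SAP 8.5.1:

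- (a) Assign 900 min only when the 15 h fast was completed.
- (b) For an earlier event-free stop, use the valid repeat allowed by protocol 8.1.1 as the value for that visit. If there is none, censor at the actual stop time and flag it as a lower bound, not an event.
- (c) State which glucose threshold defines an event for this rule, reconciling SAP 8.5.1 with SAP 4.2 and the protocol, and state that intervention means treatment for hypoglycemia.
- (d) Report the number of censored values beside each summary.

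It would also help to say in one sentence whether a deferred Week 12 challenge is tabulated at Week 12. That is a choice to record, not an error to correct.

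The cost is a few sentences and one extra table row. Challenge start and stop times are already recorded, and no study procedure changes. The downside is that a stop time is a lower bound. A post-baseline mean that uses it can be too low, by no more than the same (900 - t)/3, and a baseline value that uses it pushes the change upward. The flag and the censored count let the reader see when this applies.
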